16.2.2 Clinical outcomes

Time to steroid cessation

Time to steroid cessation, will be defined as the duration between date of randomisation and date at which participants report a current prednisolone dose of zero and there is sustained discontinuation of all steroids.

Sustained discontinuation of steroids will be defined as not taking any further steroids for the duration of follow-up.

Participants that have continued to take steroids/prednisolone to the end of follow-up or who had a temporary cessation of steroids will be censored at 18 months. Those who die, withdraw and/or are lost to follow-up will be censored at the point of death/withdrawal or loss to follow-up.

Time to steroid-free remission

Where participants report a current-oral steroid dose of zero a decision as to whether or not steroid-free remission is achieved will be agreed between the participant and physician at the week 80 assessment.

Time to PMR relapse

PMR relapse, which will be participant reported, will be defined as an increase in PMR symptoms sufficiently severe to require alteration of the steroid dosing plan. Participants will be asked every month whether they have had to adjust their planned steroid dosing plan due to an increase in PMR symptoms (participant reported relapse).

Time to PMR relapse will be defined as the duration between randomisation and date of PMR relapse. Participants that have not relapsed during follow-up will be censored at 18 months, or at date of death or withdrawal.

Note: There is no universally agreed definition of relapse in PMR, therefore, a pragmatic approach will be taken.

Number of PMR relapses

PMR relapse will be defined as an increase in PMR symptoms sufficiently severe to require alteration of the steroid dosing plan. The count of the number of PMR relapses will be derived as the sum of all relapses over the time at risk.

Time at risk will be defined as the duration between date of randomisation and the earliest of date of end of follow-up, death or withdrawal.

Cumulative (prednisolone-equivalent) steroid dose prescribed

Cumulative (prednisolone-equivalent) steroid dose prescribed over 18 months post randomisation.

The total amount of oral steroid prescribed during the trial will be assessed from GP records of all prednisolone prescriptions issued during the trial, and will be collected at 18 months post randomisation.

As for the primary outcome, if any steroid medications other than prednisolone are prescribed, these will be converted to an agreed “prednisolone equivalent dose” prior to analysis.

Safety

Adverse events (AEs) of Special Interest reported over 18 months post randomisation will include those relevant to PMR and/or investigational medicinal product.

Serious adverse events (SAEs) and SUSARs regardless of relationship to PMR or investigational product reported over 18 months post randomisation.

Glucocorticoid toxicity

Glucocorticoid toxicity is defined as per the OMERACT Glucocorticoid Core Domain Set (infection, diabetes, hypertension, fracture) adapting measures from the Glucocorticoid Toxicity Index (67)

Time to development of GCA

Time to development of GCA (defined as rheumatologist-confirmed and treated according to GCA treatment protocols specified in 2020 BSR guideline, without the diagnosis later being revised from GCA during the 18 month period) will be defined as the duration between randomisation and date of GCA diagnosis. Participants who are not diagnosed with GCA during follow-up will be censored at 18 month, or else at date of death or withdrawal.

Proportion of participants diagnosed with adrenal insufficiency

The proportion of participants who are identified as diagnosed with adrenal insufficiency will be the proportion of participants who either have a low value of 9am cortisol test, or an intermediate value followed by a positive short synacthen test, at any point during follow-up. Adrenal insufficiency screening tests (9am cortisol) will be conducted within the trial but confirmation of physician diagnosis of adrenal insufficiency, will be recorded, along with the relevant date and actions taken in response.

Deaths

Deaths from all causes over 18 months post randomisation. Date of death will be recorded, and time to death will be derived as days from randomisation to death.

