7.3 TREATMENT REGIMENS

7.3.1 Steroid management (both arms)

Participants in each arm of the trial will continue to receive usual care for their relapsing PMR, including a long-term tapering course of steroid therapy, alongside any concomitant medications that may be clinically indicated to prevent or manage steroid side-effects.

If the PMR symptoms remain well-controlled during the steroid taper without any further relapses, and the participant is able to stop taking steroid entirely, they will be able to do so just as they do in usual care.

If there is a relapse of PMR disease activity, the steroid may be re-started, or the dose may be held constant for longer than originally planned, or the dose may be escalated; as in usual care this will be individualised to the participant according to the clinical discretion of the PI.

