14.10 PARTICIPANT QUESTIONNAIRES

Participant-reported steroid dose, and whether this needed to be increased due to increase in PMR symptoms, will be collected via the Steroid Use Questionnaire. This questionnaire will be administered every four weeks from week 4 to week 80. Cumulative (prednisolone-equivalent) steroid dose will be estimated from data provided in the Steroid Use Questionnaire, interpolating if necessary. PMR relapse date(s) and date(s) of steroid cessation, if applicable, will be calculated from the data provided in the Steroid Use Questionnaire, allowing time to relapse, number of PMR relapses and time to steroid cessation and time to steroid-free remission to be calculated during the analysis of the trial.

PMR symptom severity will be captured via the PMR-IS administered at baseline (week 0) and weeks 12, 24, 36, 48, 60, 72 and 80 post randomisation.

Participant health related quality of life will be captured via the EQ-5D-5L questionnaire. This will be administered at baseline (week 0) and weeks 12, 24, 36, 48, 60, 72 and 80 post randomisation.

Participant healthcare resource use will be collected at baseline (week 0), and weeks 12, 24, 36, 48, 60, 72 and 80 post randomisation.

In addition, questionnaire booklets at baseline (week 0) and weeks 24 and 80 post baseline will include a Visual Analogue Scale (range 0 to 100mm) on which participants will mark the level of Pain they experience.

This will be used to score the PMR Activity Score. Booklets including this VAS will be distributed separately, as professional printing is required to ensure VAS lengths are exactly 100mm.

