17. STATISTICAL CONSIDERATIONS

Sample size

In UK primary care (Clinical Practice Research Datalink), patients with relapsing PMR had a mean cumulative prednisolone dose of 5g over 18 months (coefficient of variation (CV) 0.78) (68).

A clinically relevant reduction is benchmarked against the reduction likely to substantively reduce the risk of fracture or infection. Extrapolating from observational data, an average reduction in cumulative prednisolone dose of 1.5g (a reduction in mean daily dose of 2.7mg over 18 months) would be predicted to significantly reduce hip and vertebral fracture risk (69). This corresponds to a 30% reduction in cumulative dose. Our PPI group helped inform this target effect size: discussions around trade-offs revealed that most would not consider a DMARD worth it unless it could substitute for more than 2.5mg daily prednisolone over an 18-month period.

Assuming a log-normal distribution, 200 participants will provide 90% power to detect a target 30% reduction in cumulative prednisolone dose, assuming a CV of 0.78, 2-sided independent t-test for fold change (H0: mean fold change=1), 5% significance and 20% attrition (24) (nQuery v3.0). The trial will retain at least 80% power if the CV is as large as 0.94.

As part of this Australia is recruiting 50 participants there for 25% of the total number for the study.

Planned recruitment rate

Recruitment from secondary care: there will be 3 sites. Each site is expected to be open and recruiting participants over a 12-month period.

We estimate a 3:1 screen: recruitment ratio as being realistic. From the PCRN route plus referrals from rheumatologists, GPs and self- referrals, it is estimated that 150 participants will attend screening visits and 50 will be randomised in Australia.

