18.3 ANALYSIS OF SECONDARY OUTCOME MEASURES

PMR symptom severity measures, PMR activity score, and Patient-reported quality of life measures over 18 months: analysis of PMR-IS domain scores, health-related quality of life (EQ-5D-5L Utility), PMR-Activity Score will use multivariable repeated measures linear regression adjusting for minimisation factors, baseline value, treatment group, baseline-by-time interaction (if appropriate), age, time, and time-by-treatment group interaction. Centre will be fitted as a random effect, if feasible and has a positive variance component. Time will be fitted as a continuous variable, and the estimated time-by-treatment interaction effect with 95% CI and significance will be presented.

Time to steroid cessation, Time to PMR relapse: time to event will be calculated and summarised using Kaplan-Meier estimates. Adjusted hazard ratios will be estimated using Cox proportional hazards regression or parametric alternative, with covariates for minimisation factors (fitting centre as a random effect, if feasible) age and treatment group, and reported with 95% CI.

Steroid free remission at week 80 post randomisation will be summarised by treatment group and overall.

Number of relapses over time: A multivariable negative binomial regression model will be used to explore the number of relapses reported over follow-up time with an offset term for time at risk, adjusting for minimisation factors, age and treatment group. Centre random effects will be explored, assuming a Gamma distribution. Adjusted difference in rate of relapse with 95% CI will be reported.

Cumulative prednisolone-equivalent dose prescribed: A multivariable linear regression model will be fitted to log (cumulative glucocorticoid dose), adjusting for minimisation factors (fitting centre as a random effect, if feasible) age and treatment group. Adjusted mean fold difference in cumulative glucocorticoid dose with 95% CI will be reported.

Safety: The number of adverse events of special interest related to PMR or trial treatment, serious adverse events and SUSARs, in number of unique patients, will be reported by treatment received (MTX/LEF/Both/Neither) and by severity.

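### Time to steroid cessation: the censoring sentences conflict with the event definition for participants who stop, restart and stop again (read literally) and for those who stop and are then lost

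*Protocol*

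**What the plan says.** Protocol section 16.2.2 runs time to steroid cessation from randomisation to the "date at which participants report a current prednisolone dose of zero and there is sustained discontinuation of all steroids". It adds: "Sustained discontinuation of steroids will be defined as not taking any further steroids for the duration of follow-up".

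Two censoring rules follow. Participants still on steroids at the end of follow-up, "or who had a temporary cessation of steroids will be censored at 18 months". Then: "Those who die, withdraw and/or are lost to follow-up will be censored at the point of death/withdrawal or loss to follow-up". Neither rule mentions a later permanent stop, or a participant who had already stopped.

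Restarts are foreseen. Section 7.3.1 says: "If there is a relapse of PMR disease activity, the steroid may be re-started". Section 14.10 allows for more than one stop per participant: "PMR relapse date(s) and date(s) of steroid cessation, if applicable, will be calculated from the data provided in the Steroid Use Questionnaire". Section 7.4.2 collects the dose for each of the preceding four weeks on every four-weekly form.

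Section 18.3 fixes the analysis: "Time to steroid cessation, Time to PMR relapse: time to event will be calculated and summarised using Kaplan-Meier estimates", with adjusted hazard ratios from a Cox model or a parametric alternative.

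**The concern.** The event definition and the censoring sentences should sort every participant the same way. For two ordinary histories they need not.

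- **Stop, restart, final stop.** The definition gives an event at the final stop. The first censoring sentence, taken at its word, gives censoring at 18 months.
- **Stop, then death, withdrawal or loss while still off steroids.** If the duration of follow-up means the participant's own follow-up, the definition gives an event at the stop. The last sentence gives censoring at the later date, so steroid-free weeks are counted as time at risk of stopping.

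At stake is the hazard ratio for a secondary efficacy outcome. True cessations can leave the event count, and risk time can be credited to people who have already stopped. Both histories are foreseeable: every participant has relapsed at least once (section 8.1), restarts are provided for, and section 17 plans for 20% attrition.

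**Working it through.** **1. The plan's own figure.** Section 17 gives no event count, hazard ratio or power for this outcome. Its one calculation is for the primary outcome: "200 participants will provide 90% power to detect a target 30% reduction in cumulative prednisolone dose". It reproduces:

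- log-scale SD = √ln(1 + 0.78²) = 0.689
- target difference = |ln 0.7| = 0.357
- two-sided 5% t-test, 90% power: 80 evaluable per arm
- 160 / (1 − 0.20) = 200

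Nothing below touches it.

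**2. The sentences applied to two histories.**

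| History | Event definition | Censoring sentence, literally |
|---|---|---|
| A: stop week 24, restart week 32, final stop week 56, followed to week 80 | Event at week 56 | Censored at 18 months |
| B: stop week 40, lost at week 60 still off steroids | Event at week 40, if follow-up means own follow-up | Censored at week 60; 60 − 40 = 20 steroid-free weeks counted as at risk |

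In A the conflict disappears if the sentence means *only* a temporary cessation. In B it disappears if follow-up means the planned 18 months.

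**3. How often A could arise.** The share of participants off steroids at the end who had an earlier temporary stop was simulated with exponential times to week 80. All rates are assumptions.

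| Assumptions | Share |
|---|---|
| 10% restart per year, median 24 weeks to re-stop | about 4–5% |
| 30% restart per year, median 52 weeks to re-stop | about 8–9% |
| 30% restart per year, median 24 weeks to re-stop | about 13–14% |
| 50% restart per year, median 24 weeks to re-stop | about 23–25% |

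The median time to first stop was 60 or 110 weeks and mattered little.

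**4. Effect on events and hazard ratio.** A second model added arms and loss. In the control arm the median time to a stop was 40 or 60 weeks, and 30% or 50% restarted within 40 weeks of stopping. In the DMARD arm the stop rate was multiplied by 1.5 and the restart rate by 0.7. Twenty percent were lost at uniformly distributed times. Each arm had 20,000 simulated participants.

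| Rule | Control events per 100 | DMARD events per 100 | Hazard ratio |
|---|---|---|---|
| Event at final stop; stopped-then-lost are events | 34–54 | 50–70 | 1.61–1.73 |
| Earlier temporary stop censored | 28–46 | 41–60 | 1.55–1.64 |
| Stopped-then-lost censored at loss | 29–46 | 43–59 | 1.57–1.71 |
| Both sentences literal | 24–39 | 34–51 | 1.50–1.62 |

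Here 10% to 24% of final stoppers had an earlier temporary stop, and 12 to 18 of 200 participants stopped and were then lost. Scenario by scenario, the hazard ratio falls by 0.08 to 0.15 between the first and last rows (for example 1.62 to 1.54, and 1.67 to 1.52).

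**5. Which arm loses more.** This used the model in step 3 with 30% restarting per year, median 24 weeks to re-stop in both arms, and a DMARD stop rate of ×1.5. With equal restart rates, about 14% of control and 15% of DMARD final stops would be censored for an earlier temporary stop. If DMARD multiplies the restart rate by 0.7, it is about 14% against 11%. The direction depends on rates that the protocol does not give.

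**The case against.** Each conflict has a reading that removes it.

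- **A.** *Temporary* is naturally the opposite of *sustained*, and censoring applies to people without an event. On that view the sentence covers only those whose sole stops were temporary. This reading is reasonable, and probably what was meant. It stands as a limit on the point: a reader might infer a settled rule that anyone who ever paused is censored even after stopping for good, but the protocol does not say that. It fails to exclude it.
- **B.** Section 16.2.2 treats the end of follow-up as 18 months and, for relapse counts, lists death and withdrawal separately from it. So *duration of follow-up* may mean the planned 18 months, and someone lost earlier has not shown a sustained stop. But section 14.15 says participants are followed until death or the end of their follow-up period. Even on the planned-horizon reading, steroid-free weeks before loss still count as time at risk.

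Other stronger inferences fail:

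- The affected participants are censored, not counted as treatment failures.
- Section 18.1 requires an analysis plan before any comparative analysis, so it does not follow that event status will be chosen after seeing results.
- A shorter confirmation period for late stops is inherent in any endpoint sustained to the end of follow-up; adding a minimum steroid-free period is a preference.
- Eighteen months (about day 548) and week 80 (day 560) differ by 12 days, but the protocol uses them interchangeably and the visit window is two weeks either side. A Kaplan-Meier curve forced to zero would need those labels to be read as exact days.
- The figure in section 5.2 of about 50% relapsing concerns the initial taper, not restart after reaching zero, so it cannot anchor a restart rate.

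**Conclusion.** The point holds as an inconsistency in a rule that the protocol itself states. It is a literal-reading conflict for stop–restart–stop participants, and two available answers for participants who stop and are then lost, withdraw or die.

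Its size rests on assumed stop, restart and re-stop rates: roughly 4% to 25% of final cessations with an earlier temporary stop, and about 12 to 18 of 200 participants stopped and then lost at 20% attrition. In the scenarios examined, taking both sentences literally moves the hazard ratio modestly towards 1.

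A reader might infer that the arm stopping earlier must lose more of its events. That is not shown, because the direction changes with the restart rates. The consequence is confined to one secondary efficacy outcome; the primary outcome and the sample size of 200 are unaffected. It is worth correcting because section 16.2.2 fixes the rule, and an analysis plan that adopts one reading may contradict one of its sentences.

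**What to change.** Amend section 16.2.2 and carry the same wording into the SAP:

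1. Replace the temporary-cessation clause with a statement that the event is the start of the final steroid-free spell, that an earlier temporary stop does not remove it, and that participants back on steroids at their last report are censored.
2. State one classification for participants already off steroids when they die, withdraw or are lost. For example, count the event at the stop date, with a sensitivity analysis that censors them at the stop date. Either choice avoids counting steroid-free weeks as time at risk.
3. Use week 80 as the common censoring horizon, and date stops from the weekly doses in the Steroid Use Questionnaire.

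The cost is wording only, since the four-weekly forms already collect the data. The small downside of the example in item 2 is that some stops not verified to week 80 count as events; the sensitivity analysis shows how much that matters.

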6.3 SECONDARY OBJECTIVES

Secondary objectives are:

- to assess the impacts over 18 months of adding DMARD to steroids, by comparing treatment groups for:
 - PMR symptom severity (PMR-IS and sub-domains)
 - Health-related quality of life (EQ-5D-5L)
 - PMR Disease Activity (PMR-AS)
 - time to steroid cessation
 - steroid-free remission at 18 months
 - time to PMR relapse and number of PMR relapses
 - cumulative (prednisolone equivalent) steroid dose prescribed

- Safety:
 - adverse events of special interest related to investigational medicinal products or PMR
 - serious adverse events and SUSARs
 - glucocorticoid toxicity
 - diagnosis of adrenal insufficiency
 - time to diagnosis of GCA
- to estimate cost-effectiveness over 18 months post randomisation via a within-trial analysis and the long-term impact of the treatment options using a decision analytical model.
- to estimate the impact of adoption of the intervention on rheumatology service capacity

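### Steroid-free remission is stated both as a status at week 80 and as a time to event, and it is only summarised although the objective is to compare the arms

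*Protocol*

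**What the plan says.** Four places in the protocol describe this outcome.

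- **Section 6.3 (secondary objectives).** The aim is "to assess the impacts over 18 months of adding DMARD to steroids, by comparing treatment groups for" a list of outcomes that includes "steroid-free remission at 18 months". This is a status at a fixed time, and the purpose is comparative.
- **Section 16.2.2 (clinical outcomes).** The heading is "Time to steroid-free remission". The text beneath it says that, for participants reporting a zero oral steroid dose, "a decision as to whether or not steroid-free remission is achieved will be agreed between the participant and physician at the week 80 assessment".
- **Section 14.10 (participant questionnaires).** Relapse and cessation dates from the Steroid Use Questionnaire are to allow "time to steroid cessation and time to steroid-free remission to be calculated during the analysis of the trial".
- **Section 18.3 (analysis of secondary outcomes).** "Steroid free remission at week 80 post randomisation will be summarised by treatment group and overall". Nothing further is planned for remission. The time-to-event paragraph in the same section reads "Time to steroid cessation, Time to PMR relapse: time to event will be calculated and summarised using Kaplan-Meier estimates" and continues "Adjusted hazard ratios will be estimated using Cox proportional hazards regression or parametric alternative"; remission is not named there.

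**The concern.** There are two faults.

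1. **The outcome has two forms that do not fit together.** A status at week 80 and a time to event are different variables, with different analyses and different handling of dropout. The protocol promises both and fully defines neither. The time version has no event date and no censoring rule. The status version sits under a heading that says it is a time.

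2. **The analysis does not deliver the comparison that the objective promises.** Section 6.3 wants the arms compared; section 18.3 offers a summary by arm. Stopping steroids with the disease in remission matters directly to patients, and readers will set the two percentages against each other whether or not an interval is given.

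At stake is how one secondary outcome is reported. The trial is open-label and the remission decision is a joint judgement by people who know the allocation. A form and method chosen only after data have accrued would be open to the charge of selection.

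**Working it through.** **Step 1. The four statements side by side.**

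| Section | Form of the outcome | Event date and censoring | Planned contrast |
|---|---|---|---|
| 6.3 | Status at 18 months | Not needed | Arms to be compared |
| 16.2.2 | Heading: time to event; text: one decision at week 80 | None given | Not addressed |
| 14.10 | Time, calculated in the analysis | None given | Not addressed |
| 18.3 | Status at week 80 | Not needed | Summary only |

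The gap between 18 months and week 80 is not the problem: 80 × 7 / (365.25/12) = 18.4 months. The conflict is between status and time.

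**Step 2. Is the time version defined anywhere?** In 16.2.2, the entries for time to steroid cessation and time to PMR relapse each state a start at randomisation, an event and a censoring rule. The remission entry states none of these. The source named in 14.10 records doses and symptom-driven increases, not the joint participant–physician decision that defines remission. If the decision date were taken as the event date, every remission would fall at about week 80 and the times would carry almost no information.

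**Step 3. Is remission alone in having no contrast?** Efficacy outcomes under the comparative objective in 6.3, with what 18.3 states for each:

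- PMR-IS domains, EQ-5D-5L utility and PMR-AS: time-by-treatment effect with 95% CI
- Time to steroid cessation and time to relapse: adjusted hazard ratio with 95% CI
- Number of relapses: adjusted difference in rate with 95% CI
- Cumulative prescribed dose: adjusted mean fold difference with 95% CI
- Steroid-free remission: summary only

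Remission is the only exception, and no reason is given.

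**Step 4. How precise would a comparison be?** The protocol gives no figure for remission. The evaluable number comes from its primary sample size (section 17), so that is reproduced first.

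- SD on the log scale = √ln(1 + 0.78²) = 0.689; target = ln 0.70 = −0.357.
- A two-sided 5% t-test needs 80 per arm for 90% power (computed power 0.902); 160 / (1 − 0.20) = 200. With a CV of 0.94 the power is 0.804. Both stated figures reproduce.

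With 80 evaluable per arm and remission rates that are **assumptions**, half-width = 1.96 × √[(p₁(1−p₁) + p₂(1−p₂))/80], and power ≈ Φ(|p₁−p₂|/SE − 1.96):

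- 50% v 30%: SE = √[(0.25 + 0.21)/80] = 0.076; half-width 14.9 points; power about 75%.
- 45% v 30%: SE = √[(0.2475 + 0.21)/80] = 0.076; half-width 14.8 points; power about 51%.

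Over control rates of 20% to 50% with a 20-point difference, the half-width stays at about 14 to 15 points.

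**Step 5. Does the rule for missing assessments matter?** Same assumed rates, 100 randomised and 80 assessed per arm. Among those assessed: 40/80 v 24/80, a difference of 20 points. Counting unassessed participants as not in remission: 40/100 v 24/100, a difference of 16 points. The rule moves the estimate by 4 points, so it has to be stated.

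**The case against.** The strongest reply has three parts.

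**The time label has no analytic consequence.** Sections 6.3 and 18.3 agree on a fixed-time status, and no planned analysis uses a time to remission. What remains is stray wording in a heading and a list. This stands, and it is why the first fault is a matter of wording. A reader might go further and infer that a time to remission cannot be computed at all. The documents do not support that: cessation dates come from four-weekly questionnaires, so remission confirmed at week 80 could be dated back to sustained cessation. No section states that rule. The time is undefined, not impossible, and dated that way it would largely repeat time to steroid cessation.

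**The analysis plan may supply the contrast.** Section 18.1 says that all analyses will be predefined there, and that plan is not shown. A reader might infer that the objective will go unanswered, or that an interval is ruled out. Neither follows: the summary is by arm, so the arms appear side by side, and nothing forbids an interval. But the protocol is not silent. It names a method for this outcome, and that method falls short of its own objective while every neighbouring outcome gets an estimate.

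**Description may suit a soft outcome.** Remission is a joint judgement with no stated criteria, made in an open-label trial. That would be a fair reason to treat it as descriptive, but section 6.3 lists it for comparison. Lack of blinding is explained in section 7.1 and affects other outcomes too, so it is not a defect of this item in particular.

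The remission rates used above are assumptions. They show that a comparison would be feasible but imprecise; they do not measure harm from the present wording.

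**Conclusion.** The point holds in a limited form. The protocol states steroid-free remission as a fixed-time status in 6.3 and 18.3 and as a time to event in 16.2.2 and 14.10, without defining the time. Section 18.3 only summarises it although 6.3 lists it for comparison, which makes it the only efficacy outcome under that objective with no stated estimate and 95% confidence interval.

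The conclusion rests on the wording of those four sections, not on the illustrative rates. The effect is confined to one secondary outcome: the primary analysis, alpha and the sample size of 200 are unaffected. It should be corrected because the change is cheap and the present text leaves the choice of form open in an unblinded trial.

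**What to change.** 1. **Sections 16.2.2 and 14.10.** Delete *time to* for this outcome. Define it as steroid-free remission at week 80, yes or no, and say that anyone not reporting a zero dose counts as no.
2. **Section 18.3.** Replace the summary with a between-arm estimate and 95% confidence interval in the intention-to-treat population. One suitable choice is logistic regression adjusted for the minimisation factors and age, with centre handled as for the other secondary outcomes, reported as an adjusted risk difference or odds ratio.
3. **Section 18.3.** State how participants who die, withdraw or miss the week-80 assessment are counted.
4. **Optional.** Because the judgement is unblinded, add a supporting analysis of self-reported zero dose at week 80.

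If the sponsor does not want a comparison, rewording 6.3 to make remission descriptive would also remove the mismatch. If a time variable is wanted, its event date and censoring rule must be written down and an analysis named.

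The cost is a few lines of protocol text and one regression on data already collected. No extra visits, data items or participants are needed.
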